6.2.3 Blinding

This study is a single blinded trial. Every effort will be made to maintain masking until the study's completion of treatment of the 152 subjects in the RCT. Investigators involved in analyzing fMRIs, Co-Is, other than [name], participating in the RCT, study personnel performing data entry and the study statistician will be blinded to knowledge of subjects' treatment groups. Investigator blinding will only be breached if a subject suffers an unexpected clinical event and investigator knowledge of the subject's treatment is essential to providing standard of care. Subjects cannot be blinded to treatment interventions as it will be obvious to them whether or not they are undergoing hypnotherapy or taking medications.

6.2.4 Treatment Visits

Treatment Visits (weeks 1-8) Depending on randomization, participants will either undergo medication counseling sessions or hypnotherapy sessions. These visits are expected to be initiated within one month following randomization with the goal of initiating treatment within 1 week of randomization. However, subjects will be given the necessary time to prepare for their upcoming weekly treatment sessions. These visits are expected to be completed within 8 weeks of initiation of the first treatment.

The number of sessions attended by subjects will be recorded. The Medication side effects/incontinence log and the Hypnotherapy CD-digital recording use/incontinence logs will be collected at the visits. Please refer to section 5 for details.

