 $\sqrt{}$ Study Visits #3-10 (or #4-11): 8 hypnotherapy sessions Study Visits #3-10 (or #4-11): 8 Pharmacotherapy sessions over 2 months. CD logs documenting home practice over 2 months. Medication logs gathered weekly and sent gathered weekly/sent to coordinator. Session(s) taped to study coordinator. Session(s) taped for quality for quality assurance and randomly audited. assurance and randomly audited. Study Visit #12: (for pts who had a Study Visit #12: (for pts who had a baseline fMRI & same procedure baseline fMRI & same procedure as as Visit #3): F/U fMRI performed Visit #3) F/U fMRI performed and and have urine and vaginal swab have urine and vaginal swab samples samples collected and stored for collected and stored for possible possible future analysis. future analysis.

Study Visit #11 (or #13): Final Research Coordinator Meeting with patients after treatment finished (approx. 2-3 months after randomization); f/u questionnaires administered (OABq-SF,ISI, PBBC, PISQ-12, CRADI-8,IBS Module, BPIC questionnaire, Post-treatment Expectation question), voiding diary and treatment compliance information collected. Urine may be collected and stored for possible future analysis. Plans for f/u explained & Contact information re-confirmed. Pt incentives given

6 mo. f/u with patients after treatment finished (approx. 6 months after treatment & may be phone/mail f/u): f/u questionnaires administered (OABq-SF, ISI,PPBC, PISQ-12, CRADI-8, IBS Module, BPIC, Post-treatment Expectation), voiding diary and treatment compliance information collected. Plans for f/u explained & Pt incentives given/mailed. Arrangements made for hypnotherapy patients who choose optional additional hypnotherapy session prior to 12-mo follow-up.

12 mo. f/u with patients after tx finished (approx. 12 months after tx & may be phone f/u): f/u questionnaires administered (OABq-SF, ISI,PPBC, PISQ-12, CRADI-8,IBS Module, BPIC, Post treatment Expectation question), voiding diary and treatment compliance information collected. Pts thanked and Pt incentives given/mailed

Flow Diagram 2--- for fMRI Normative Controls:

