instructed to not use the patients' name or any other identifiers during the recorded session. Subjects will be scheduled for in person visits with the medication counselor who will review medications and their side effects. However, if subjects state these in person visits are overly burdensome, these visits may occur via phone as long as the patient comes in for at least 2 of the subsequent visits for pill dispensation which should occur midway and at the end of the 8 sessions. These sessions will take as long as required/desired for subjects to feel that they have received adequate instruction/counseling. Discussion of strategies to cope with their bladder symptoms will occur. The expected side effects of medications (such as dry mouth, constipation) will be discussed and strategies to cope with side effects will also occur. It is expected that these sessions will take approximately 20-60 minutes, depending on the subjects' needs. The medication may be modified if the patient complains of side-effects from the initial anti-cholinergic or perceives that her response in UUI treatment is inadequate; a different anti-cholinergic may be given to the patient if she requests a different UUI medication. The study will use either of two standard, long acting anti-cholinergic medications and dosages (Long acting Tolterodine 4mg/day or Extended Release Oxybutynin 10 mg/day or their equivalent generic substitutes). Initial medication use will usually be Oxybutynin 10 mg/day but will depend on the patient history (for example those who have used Oxybutynin unsuccessfully will be given Tolterodine and vice versa). A recent AHRQ metaanalysis found that there was no difference in effectiveness or side-effects between the available anticholinergics used to treat UUI as long as the medications were extended release formulations, such as those used in this study.³⁸ The details of these sessions are in the "Pharmacotherapy Session Guidelines" (see Attached MOP). Following the 8 weeks of therapy as described previously, subjects will continue to take their anti-cholinergic medications and continued use of medication will be tracked for the 1 year duration of the study.

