Potential adverse effects of pharmacotherapy: Subjects randomized to pharmacotherapy will be instructed take a standard anticholinergic extended release dose (see above) for urgency incontinence. Subjects with major contraindications to anticholinergic medications will be excluded from study participation (see exclusion criteria). Serious adverse events related to anticholinergic medications are rare, however mild side-effects are relatively common; these include dry mouth, constipation, dyspepsia or mild nausea, dry eyes, and change in urination such as urinary hesitancy.^{38,54} Subjects in this proposal will be informed regarding potential side effects of medications, will keep medication logs and will regularly meet with a medication counselor to review these side effects. Minor side effects may include symptoms such as dry mouth, dry eyes or constipation. The original anticholinergic may be changed to a different long acting anti-cholinergic for UUI if the patient finds the minor side effects to be bothersome and wishes to change medications. Serious medication related adverse events occur the medication will be discontinued (see protection against risks below). If subjects report urinary retention or other symptoms of concern to the medication counselor, subjects will be instructed to stop the medication. Simultaneously a clinic visit to the UNM Urogynecology Clinic will be arranged so that subjects may be appropriately evaluated. These measures will decrease the risk of harm from study participation.

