'False Memory Syndrome' and severe emotional upset--- Relevant background, management and modification of intervention or participant assessments: Although, in the 1980s 'false memory syndrome' was described with the use of hypnotherapy in child abuse survivors, the current practice of hypnotherapy uses a much different approach to this therapeutic application. Current practice includes open-ended lines of questioning as opposed to suggestive or leading lines of questioning utilized in the 1980s with these victims. Transformation of hypnotherapy practices has greatly decreased occurrence of false memory syndrome. Recently, the hypermnesia attributed to the hypnotic state has been rejected based on more rigorous research.²² Last, the use of hypnotherapy in this study is for UUI treatment and recall of emotionally traumatic events will not be part of the hypnotherapy protocol. Thus, serious risk to subjects undergoing hypnotherapy for UUI is negligible. If a subject reports severe emotional upset attributed to the sessions, her sessions will be terminated. In the unlikely event that >33% of study subjects report that they experience serious emotional upset from study participation the study will be suspended and a review will occur. If these events are found to be attributable to hypnotherapy, the study will continue to be suspended until the hypnotherapy protocol is re-evaluated and revised (see below). Serious emotional upset includes inability to work or events that would necessitate evaluation by a physician or care provider. It is highly unlikely that hypnotherapy would unmask or de-repress significant emotional upset (e.g. hysteria, uncontrollable anger or hostility) in subjects. The potential for this occurring will be minimized by excluding subjects with a history of schizophrenia or untreated bipolar disorder and by having the hypnotherapist guide the sessions and terminate sessions if subjects are beginning to show signs of undue duress during hypnotherapy. Although other hypnotherapy studies have not reported significant

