7.4 Reporting Procedures

Monitoring of Adverse Events & Frequency of Periodic Observations & Reporting & Follow-up: Adverse events will be monitored by spontaneous subject report and subject interviews and data review. At each clinic visit or follow-up telephone call, subjects will be asked to recall any adverse events since the time of their last contact (either via phone call, in-person clinic or study visit). The Study Coordinator (or her surrogate in her absence) will record the information using a standardized format and report the data to the PI's. If the AE is a reportable event as defined by the UNM HRPO (i.e. meets all the following criteria; it was unanticipated, caused harm or placed a person at increased risk of harm, and was more likely than not to have been related to the research) it will also be reported to the UNM HRPO (see UNM HRPO "Event form" attached which must be signed by the DSMB. The UNM HRPO will be notified of reportable events as soon as possible and within 5 days of the event date or

the "site awareness" date. AEs will be followed until they are resolved or considered stable, typically for one month, although this time will be extended to up to 4-6 months, depending on the instability of the event.

SAEs will be immediately (i.e. as soon as the Investigators or Study personnel are made aware that an SAE occurred) reported to the UNM IRB (HRPO) as per IRB guidelines and the NIH Project Officer and addressed by the DSMB if determined to be attributable to study participation (see SAEs below).

A Data Safety and Monitoring Board has been identified for this study. AE reports will be generated using standard forms, including the Adverse Event Case Report Form and Serious Adverse Event Case Report Form (see attached). The DSMB will meet quarterly for the first year and the DSMB will reassess and determine whether observations can be reviewed semi-annually thereafter. During the DSMP formal meetings the events will be reviewed. The severity of the event will be determined and an action plan to avoid recurrence of events (if found to be attributable to study participation) will be formulated and implemented. Research related adverse events will be reviewed and annual reports which include AE reports, subject enrollment/withdrawals and protocol violations will be generated for the University of New Mexico Health Sciences Center Human Research Protections Office (HRPO), Data Safety Monitoring Board and NCCAM/NCCAM Project Officer.

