preventable, and develop an action plan to prevent recurrence including potential protocol revision and this report will be given the DSMB. The likelihood of this occurring is very small. Sporadic occurrence of emotional upset is always possible in any setting, and if an individual treated with hypnotherapy notes this occurrence which she attributes to hypnotherapy, the intervention will be terminated. However, we believe that if a third of subjects complain of this issue, the study should be halted until the circumstances surrounding its occurrence are investigated. Other hypnotherapy studies have not reported this occurring; however, we believe that it is prudent to consider this as a possibility and to prepare for it as a possibility, although highly unlikely. The study would also be stopped if there were statistically significant differences in SAEs (as defined in section 7.3) definitely attributable to the interventions (hypnotherapy or pharmacotherapy). The medications in the pharmacotherapy arm, considered standard of care treatments, have undergone rigorous FDA approval, and it would be highly unlikely that these events would occur.

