10.2 Data Management

Data will be collected on CRFs approved by the UNMH HRPO including demographic and patient history forms, eligibility forms, questionnaires, Cystometrics and fMRI task data sheets, pharmacotherapy side effect and hypnotherapy practice logs, treatment compliance logs as well as forms related to AE tracking. These data will be maintained as noted above by the Investigators and Research personnel. The database used by the UNM Urogynecology research team will be password protected. The database will be built using the web-based platform, REDCap®, as recommended by the UNM CTSC. The study's data entry personnel will receive only coded information that is entered into the database under those identification numbers. Only coded information without unique patient identifiers will be entered into the study database. Only study personnel will have access to individually identifiable private information and data. Confidentiality will be maintained by keeping paper-based study subject folders for all enrolled subjects in a locked cabinet in the Urogynecology research area (this folder will include case report forms, laboratory reports, guestionnaires, voiding diaries, intake forms). Consents will be kept separate from these research folders and will be kept in a separate locked cabinet in the UNM Research Administrative area. A separate log linking patient codes and unique patient identifiers will be kept on password protected computer available only to study personnel. CRFs will include forms used to collect subject information including demographic, medical history forms, questionnaires, compliance forms, fMRI screening forms, inclusion and exclusion criteria forms as well as patient behavioral therapy instruction handouts.

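### Non-serious adverse events are sought more intensively on drug than on hypnotherapy, so between-arm comparisons of their rates may be biased toward an apparent excess on drug

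*Combined protocol and SAP*

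**What the plan says.** **Arm-specific collection.** Section 6.2.4 describes the logs for the eight treatment weeks: "The Medication side effects/incontinence log and the Hypnotherapy CD-digital recording use/incontinence logs will be collected at the visits". Section 10.2 repeats the split among the data to be collected: "pharmacotherapy side effect and hypnotherapy practice logs". Flow Diagram 1 (section 3) shows both logs being collected weekly. Under the adverse effects of pharmacotherapy, section 5.1 says that drug-arm women "will keep medication logs and will regularly meet with a medication counselor to review these side effects". The same section says of the counseling sessions: "The expected side effects of medications (such as dry mouth, constipation) will be discussed and strategies to cope with side effects will also occur". The accounts of the hypnotherapy sessions in sections 3 and 5.1 mention no symptom enquiry beyond asking about phobias and fears at the first session.

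**Common collection.** Section 7.4 applies to both arms: at each clinic visit or follow-up call, "subjects will be asked to recall any adverse events since the time of their last contact". It also relies on spontaneous report and data review. Section 7.3 requires AEs to be recorded whatever their relationship to treatment. Table 1 marks AEs at all eight treatment visits and every follow-up, without a split by arm. Sections 7.1 and 7.2 name one Frequency of Specific Events Table covering both anticholinergic symptoms and severe emotional upset. The CRADI-8 and IBS Module are given to both arms at baseline and at 2, 6 and 12 months.

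**Use of harms data.** Section 9.4 would stop the study "if there were statistically significant differences in SAEs (as defined in section 7.3) definitely attributable to the interventions". The table in section 10.3.5 sends AEs and their rates to the DSMB. No test of non-serious AE rates between arms is specified.

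**The concern.** A weekly written prompt, together with a counselor who raises dry mouth and constipation by name, can be expected to elicit more mild symptoms than a general recall question. If only one arm has the prompt, recorded rates of non-serious events can differ even where true rates are equal, and the difference would favour hypnotherapy.

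This matters because tolerability is part of the case for the trial. Section 2.1 describes the medications as poorly tolerated and cites pilot and case-series evidence that hypnotherapy is well tolerated. A tolerability contrast in the report is foreseeable although it is not a listed objective, and the DSMB will see AE rates during the trial. Since the drugs do cause some of these symptoms, a true excess and an ascertainment excess would be mixed together, and the data as collected could not separate them.

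**Working it through.** The documents state no AE rate, detection rate or power for harms, so there is no plan figure to reproduce. The check has two parts.

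**1. Sources of AE information, side by side**

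| Source | Drug | Hypnotherapy |
|---|---|---|
| Weekly log (6.2.4, 10.2) | side effects, incontinence | recording use, incontinence |
| Session review of named symptoms (5.1) | yes | none described |
| AE enquiry at each contact (7.4) | yes | yes |
| All AEs recorded whatever the relationship (7.3) | yes | yes |
| AE row in Table 1 | all visits | all visits |
| CRADI-8 and IBS Module | baseline, 2, 6, 12 months | baseline, 2, 6, 12 months |

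The last four rows are equal and the first two are not. The section 7.3 rule governs an event once it is known, not how it comes to be known. The bowel questionnaires do not cover dry mouth, dry eyes or hesitancy.

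Two details bear on the common enquiry. Section 7.4 has the coordinator or her surrogate record AEs, while section 5.1 places hypnotherapy sessions in the hypnotherapists' own offices, and the documents do not say who asks about AEs there. Section 7.4 also counts data review as a source, and nothing keeps drug-log entries from reaching the AE form by that route.

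**2. What unequal detection could do (assumed inputs)**

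Inputs: 152 randomized, about half per arm, so n = 152/2 = 76. The true risk t of any listed symptom is taken as equal in both arms, from 10% to 50%. Detection on drug is assumed to be d₁ = 0.90, and on hypnotherapy d₂ = 0.80, 0.70 or 0.50.

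- Recorded risks: p₁ = t·d₁ and p₂ = t·d₂.
- Recorded risk ratio: d₁/d₂, which does not depend on t.
- Chance of a falsely significant drug excess (two-sided 0.05): Φ{[(p₁ − p₂) − 1.96·s₀]/s₁}, with s₀ = √[2p̄(1 − p̄)/n], s₁ = √{[p₁(1 − p₁) + p₂(1 − p₂)]/n} and p̄ = (p₁ + p₂)/2.

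Worked case, t = 0.30 and d₂ = 0.70: p₁ = 0.27, p₂ = 0.21, difference 0.06, s₀ = 0.0693, s₁ = 0.0691. Then (0.06 − 0.1358)/0.0691 = −1.10, and Φ = 0.136.

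| d₂ | Risk ratio | Difference, t = 10% to 50% | Chance of false drug excess, t = 10% to 50% |
|---|---|---|---|
| 0.90 | 1.00 | 0 | 2.5% |
| 0.80 | 0.90/0.80 = 1.13 | 1 to 5 points | 4% to 9% |
| 0.70 | 0.90/0.70 = 1.29 | 2 to 10 points | 7% to 24% |
| 0.50 | 0.90/0.50 = 1.80 | 4 to 20 points | 16% to 74% |

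The range runs from negligible to large, and nothing in the documents places the trial within it. Fewer women analysed would lower the chance of significance but leave the risk ratio unchanged.

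**The case against.** The strongest reply is that AE capture does not rest on the logs. Every woman is asked at every contact, all AEs are recorded, and one events table names the important harms of both treatments. The drug log also serves drug management, because reported side effects can lead to a change of medication. The only formal between-arm harm rule concerns SAEs, the plan makes no tolerability claim, and the log forms and session guidelines are in a manual that is not among the documents, so symptom prompts in the hypnotherapy arm cannot be excluded.

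Much of this stands, and it rules out several stronger readings that a reader might infer:

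- *Hypnotherapy harms go uncollected, or drug harms are over-counted.* Neither is shown. Severe emotional upset and recording use while driving are named for tracking (sections 7 and 7.1), and prompting makes drug-arm capture more complete rather than false.
- *The SAE stopping rule is compromised.* It is limited to SAEs definitely attributed to treatment, and serious events depend less on prompting. Dry mouth or constipation in a log would not ordinarily feed it.
- *The drug arm is the reference rate for judging emotional upset.* Section 7 says "If these events are found to be attributable to hypnotherapy, the study will continue to be suspended", but the route described is review and a report to the DSMB, not a comparison of arm rates. The trigger counts all study subjects, section 7 lists emotional distress as a study-wide risk, and no text says that the drug log asks about upset. If listing upset under hypnotherapy had any effect, it would run the other way.

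What the reply does not remove is the prompted layer that only the drug arm is described as having.

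**Conclusion.** The point holds as differential ascertainment of non-serious AEs. Drug-arm women have a weekly side-effect log and counselor review of named symptoms; hypnotherapy women have a practice log and the enquiry common to both arms. Between-arm rates of mild events may therefore be biased toward an apparent excess on drug.

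The conclusion assumes that prompting finds more mild symptoms than general recall, and that the manual adds no equivalent prompt for hypnotherapy. The size is unknown, and the risk ratios of 1.13 to 1.80 are illustrations. No efficacy outcome is defined on the log's side-effect entries, and the consequence for the SAE rule is likely small.

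**What to change.** Section 11.2 says that enrollment is complete, so the main workable change is to the analysis:

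1. State in section 9.6 that any between-arm comparison of harms uses events captured by the procedure common to both arms: the AE form and enquiry at each contact, and the CRADI-8 and IBS Module for bowel symptoms.
2. Flag each AE as solicited by the drug log or counselor, or as captured by the common enquiry. Fix beforehand how an event found by both routes is classified.
3. Report drug-log symptoms descriptively, for the drug arm only.
4. Give the DSMB the AE rates split in the same way.

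This reduces the bias without fully removing it, since keeping a log may also sharpen a woman's answers to the common enquiry. The report should say so.

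For any women still to be treated or followed, use one identical symptom checklist in both arms' weekly logs and at follow-up, covering the listed drug symptoms, urinary infection symptoms and emotional upset. It should add to spontaneous reports and case review, not replace them; attribution of emotional upset should continue to draw on all of these.

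The cost is a minute or two per woman per week for the checklist, a paragraph of SAP wording, and a little more analysis work. No new visit is needed.
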